6.3 Screen Failures

Screen failures are defined as participants who consent to participate in the clinical trial but are not subsequently randomly assigned to the study intervention or entered in the study. A minimal set of screen failure information is required to ensure transparent reporting of screen failure participants to meet the Consolidated Standards of Reporting Trials (CONSORT) publishing requirements (for NIH studies) and to respond to queries from regulatory authorities. Minimal information includes demography, screen failure details, eligibility criteria, and any serious adverse event (SAE).

6.4 Lifestyle Considerations

Females must abstain from sex or use a highly effective method of contraception during the period from Screening to administration of study drug and for 30 days after the last dose of study medication. Standard acceptable methods include abstinence or the use of a highly effective method of contraception, including; hormonal contraception, diaphragm, cervical cap, vaginal sponge, condom with spermicide, vasectomy, intrauterine device. If females are of non-child bearing potential, they must be post-menopausal defined as: age > 55 with no menses within the past 12 months, or history of hysterectomy, or history of bilateral oophorectomy, or bilateral tubal ligation.

Males must consent to use a medically acceptable method of contraception throughout the entire study period and for 90 days after their last study drug application. They must agree to not donate sperm for 90 days after their last study drug application.

Subjects will be advised not to drive or operate machinery until they have gained sufficient experience on study drug.

7 STUDY INTERVENTION

7.1 Description of Study Intervention(s)

Product with description, all names, dosage form	Potency	Investigational or Standard of Care (SOC)	Packaging/Appearance	Manufacturer	Storage Conditions
Case – 99.99% pure cannabidiol (CBD) with 100% Pure USDA Organic Shea Butter	6.2 mg/mL	Investigational	Placed within 10mL syringe labeled with approved institutional labeling for research use only.	Eco-X, Inc, Grand Junction, CO (CBD) Mary Taylor Naturals, LLC, Fort Myers, FL (Shea Butter)	Room Temperature
Control – 100% Pure USDA Organic Shea Butter	N/A	Investigational	Placed within 10mL syringe labeled with approved institutional labeling for research use only.	Mary Taylor Naturals, LLC, Fort Myers, FL	Room Temperature

7.2 Dosing and Administration

Subjects will be randomized to receive a total of 28mL of either 6.2 mg/mL of CBD with Shea butter or Shea butter alone placed within three (3) 10mL syringes. Subjects will be advised to apply 1 mL of the cream overlying their thumb basal joint dorsally twice daily, approximately every 12 hours. In the CBD condition, the cream will be formulated to deliver approximately 12.4 mg of purified CBD per day, whereas in the control condition the Shea butter will be utilized alone. The purified CBD is colorless and odorless to facilitate blinding.

The CBD with Shea Butter or Shea butter alone will be provided to subjects in 10 mL syringes without a needle, with a rubber topper. Subjects will be instructed to store the cream at room temperature. Subjects may dispense the cream from the syringe into a gloved hand. Gloves will be provided to the subject along with the investigational product. The cream will need to be applied to the base of the thumb until completely absorbed. Subjects should avoid water to the area for at least one hour.

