
To determine the safety of treatment CBD.
	
Safety will be determined by evaluating:
 
 • The frequency and severity of adverse events from the beginning of treatment through the end of study participation. • Changes in skin appearance from baseline using standardized skin assessment tool. (patient will be removed from study with a score ≥ 2) • Clinically significant change in CBC (baseline and follow-up) • Clinically significant change in basic metabolic panel (i.e., BUN, creatinine, CO₂, Cl, K, Na, and glucose) (baseline and weekly follow-up) • Clinically significant change in hepatic function testing (i.e., serum transaminases [ALT/AST], total bilirubin, and alkaline phosphatase) (baseline and weekly follow-up) • Clinically significant change in vital sign assessments (i.e., heart rate and blood pressure) (baseline and weekly follow-up) • Suicidal behavior and thoughts as a specific question using the Columbia-Suicide Severity Rating Scale (C-SSRS) (baseline and weekly follow-up)
--	--

Study Population: 40 subjects with presenting with thumb basal joint arthritis over the age of 18 will be recruited from the UVA Hand Center.

Description of Sites/Facilities This will be a single-site study conducted at the UVA Hand Center at the University of Virginia.

Enrolling**Participants:****Description of****Study****Intervention:**

[figure not shown]
The study design will be a double-blind randomized control trial with crossover. Treatment will be blinded to the subjects and investigators. Patients will be randomly assigned two (2) weeks of the case (CBD) or control cream and then crossover to the other cream for two (2) additional weeks. Patients will apply the topical cream at their thumb basal joint twice daily for 1 hour. The subjects will be advised to observe for physiologic changes, skin changes, or other adverse effects. If mild to serious adverse events are noticed, the creams will be removed immediately and appropriate care and observation will be taken. Each condition will last for 2 weeks and then subjects will be contacted by the study coordinator to facilitate crossover into the other condition. To capture any delayed-onset adverse events, including those related to skin changes that might develop after the drug is discontinued, subjects will attend a follow-up visit seven (7) days following the last dose of investigational cream.

Study**Duration:****Participant****Duration:**

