5 STUDY DESIGN

5.1 Overall Design

The study design will be a double-blind randomized controlled trial with crossover. Treatment will be blinded to the subjects and investigators. Patients will be randomly

assigned two (2) weeks of the case or control topical cream and then crossover to the other cream for two (2) more weeks. Patients will apply the cream at their thumb basal joint twice daily for one (1) hour. The subjects will be advised to observe for physiologic changes, skin changes, or other adverse effects. If mild to severe drug-related adverse events are noticed, the creams will be removed immediately and appropriate care and observation will be taken. Each condition will last for two (2) weeks and then subjects will be contacted by the study coordinator to facilitate crossover into the other condition. This study will last one year from the beginning of subject recruitment to data analysis. Subjects will be enrolled in this study for approximately six (6) weeks from Screening until the final Study Visit.

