7.3 Preparation/Handling/Storage/Accountability

7.3.1 Acquisition and Accountability

The investigational drugs (CBD with Shea butter and Shea butter control) will be stored in a secure area within the UVA Hand Center. Study drug accountability will be maintained by the research team. The investigational drugs will be distributed to the subjects by the study team and are returned to the study team at the next visit. Any remaining investigational drugs will be destroyed in accord with institutional policies.

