14 APPENDICES

14.1 Schedule of Activities (SoA)

Visit	Visit 1 (Screening and Baseline)	Visit 2 (Baseline)	Visit 3	Visit 4	Visit 5	Visit 6	Visit 7
Study Day	-7 ¹	0	7 (+/- 1)	14 (+/- 1)	21 (+/- 1)	28 (+/- 1)	35 (+/- 1)
Informed Consent	X						
Review study eligibility	X						
Blood Draw ²	X ³						X
Urine Pregnancy Test (if applicable)	X	X					
Hand Functional Assessment		X	X	X	X	X	
Patient Reported Outcome Measures		X	X	X	X	X	
Physician Skin Monitoring		X	X	X	X	X	X
Columbia- Suicide Severity Rating Scale	X	X	X	X	X	X	X

¹ Screening may take place within one week of baseline visit to allow for results of bloodwork and pregnancy testing.

² Blood pregnancy test to be ordered during screening visit only.

³ Baseline blood testing (Hemoglobin and Platelet count, Creatinine, AST/ALT) will be obtained at the screening blood draw.

Monitor for somnolence and sedation			X	X	X	X	X
Study Medication Dispensed		X		X			
Diary dispensed		X		X			
Diary Review			X	X	X	X	X
Study Medication Collected			X	X	X	X	
Assessment of Adverse Events		X	X	X	X	X	X

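### The 28 mL supplied per condition is right for 14 days but has no margin, while the visit windows allow 15-day periods, so a subject who misses no dose and is seen a day late is assessed about 24–36 h after the last application.

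*Combined protocol and SAP*

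**What the plan says.** Section 7.2 sets the supply: "Subjects will be randomized to receive a total of 28mL of either 6.2 mg/mL of CBD with Shea butter or Shea butter alone". The same section puts this volume into three syringes of 10 mL each. Subjects are to "apply 1 mL of the cream overlying their thumb basal joint dorsally twice daily, approximately every 12 hours". Section 7.2 does not say that 28 mL is the amount per condition. That follows from the arithmetic and from the two dispensing visits.

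Section 1.1 fixes the length of a condition: "Patients will be randomly assigned two (2) weeks of the case (CBD) or control cream". Section 5.1 agrees: "Each condition will last for two (2) weeks and then subjects will be contacted by the study coordinator".

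In the Schedule of Activities (section 14.1), the row "Study Medication Dispensed" is marked only at Visit 2 (Day 0) and Visit 4. Visit 4 is allowed on Day 13 to 15 and Visit 6 on Day 27 to 29. Section 9.1 places hand function and PROMIS assessments at baseline and on Days 7, 14, 21 and 28.

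The documents state no overage, no resupply, no instruction on dosing when a visit runs late, no limit on the time from last application to assessment, and no rule on whether windows run from Day 0 or from the preceding visit.

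**The concern.** The supply is cut to exactly 14 days, but the visit that closes a period may fall later. On Day 15 a subject who has used every dose on time has no cream left for the final day. Days 14 and 28 are the last hand function and PROMIS measurements under each condition. Some of them could therefore be taken a day or more off treatment, although the schedule calls for an application about every 12 hours. The subjects exposed to this are those who adhere best.

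If the effect of topical CBD fades within a day or two, those measurements would understate it, and the within-subject contrast would be diluted. The documents give no offset time, so the amount cannot be worked out from them.

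**Working it through.** **Inputs.** Volume 28 mL, dose 1 mL twice daily about every 12 h, strength 6.2 mg/mL, three 10 mL syringes (7.2). Nominal period 14 days (1.1, 5.1). Visit 4 on Day 13–15, Visit 6 on Day 27–29, dispensing at Visits 2 and 4 (14.1). The time of the first application is not stated, so I take a range from the dispensing visit itself (0 h) to 12 h later.

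**The plan's own figures.** 1 mL × 2 per day × 14 days = 28 mL, and 2 × 6.2 = 12.4 mg CBD per day, as 7.2 states. Both reproduce. Margin at 14 days: 28 − 28 = 0 mL.

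**Permitted period lengths.**
- Period 1: 13 to 15 days.
- Period 2, windows counted from Day 0: shortest 27 − 15 = 12 days, longest 29 − 13 = 16 days. Of the 9 Visit 4/Visit 6 pairs, 3 exceed 14 days: (13, 28) and (14, 29) at 15 days, (13, 29) at 16 days.
- Period 2, counted from the actual Visit 4: 13 to 15 days.

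These count permitted days. They are not expected frequencies.

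**Time from last available application to the visit, no dose missed.** The 28th application falls at 27 × 12 = 324 h if the first is at dispensing, or 28 × 12 = 336 h if the first is 12 h later. The volumes assume dosing continues up to the visit.

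| Period | Visit at | Volume for dosing to the visit | Short of 28 mL | Gap, first dose at 0 h | Gap, first dose at 12 h |
|---|---|---|---|---|---|
| 14 days | 336 h | 28 mL | 0 | 12 h | 0 h |
| 15 days | 360 h | 30 mL | 2 mL | 36 h | 24 h |
| 16 days | 384 h | 32 mL | 4 mL | 60 h | 48 h |

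**With missed doses.** Each missed dose leaves 1 mL for a later slot and shortens the gap by 12 h, down to the ordinary 12 h. At 15 days, one missed dose gives 36 − 12 = 24 h or 24 − 12 = 12 h. Two missed of 30 (28/30 = 93.3% adherence) remove the shortfall at 15 days, and four of 32 (28/32 = 87.5%) remove it at 16 days.

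**Ceiling on the effect.** Each subject has one end-of-period CBD assessment. If all 40 complete, effects are equal and one affected subject has lost the whole effect by the visit, the mean CBD effect at that time point falls by 1/40 = 2.5%. If the effect outlasts the gap, the fall is 0. This is on the mean scale and only indicative, because section 11.1 plans a Wilcoxon signed-rank test.

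**The case against.** The strongest reply is that the course is two weeks by definition, 28 mL is a full two-week course, and the +/- 1 day is only flexibility for the visit. On that reading nothing is short, and a subject who stops at 14 days has the same gap at a late visit however much cream was supplied. This stands. It means that extra cream alone does not close the gap. It does not remove the gap, since the assessment is still a day or more after the last dose.

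Several stronger readings are tempting and are not supported:
- A reader might infer that 28 mL is a calculation error. It is not, as it reproduces exactly.
- A reader might infer that nearly adherent subjects in general are assessed 24–60 h after the last dose. That range needs no missed dose at all, and 60 h also needs windows counted from Day 0, Visit 4 on Day 13, Visit 6 on Day 29 and a first application at the dispensing visit.
- A reader might infer a bias in favour of CBD. Both creams have the same limit, and a one-day-late visit can occur in either period, so noise or dilution is the more likely result.
- A reader might infer that the primary time point is compromised. The documents do not single out Day 14 or Day 28 as primary.

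It is also fair to say that long periods can be found afterwards from visit dates and returned syringes. Section 7.3.1 says: "The investigational drugs will be distributed to the subjects by the study team and are returned to the study team at the next visit". A sensitivity analysis without them is therefore possible with data already planned.

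**Conclusion.** The mismatch is real and minor. The supply has zero margin at 14 days, while the schedule permits 15-day periods in both conditions. For a subject who misses no dose, a 15-day period means assessment about 24–36 h after the last available application instead of 12 h or less. The 16-day case (48–60 h) is a corner case of period 2. The possible consequence is a slight dilution of the contrast at Days 14 and 28. Its size is unknown, because the documents give neither the frequency of late visits nor the time for which an effect lasts.

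This rests on three assumptions: 28 mL is the supply per condition; the first application falls 0 to 12 h after dispensing; and cream collected at Visits 3 and 5 is handed back the same day, since no dispensing is marked there. I would treat it as a cheap improvement and not as a flaw that threatens the trial's conclusions.

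**What to change.** Three changes, made together:
1. In 7.2, fill the existing three 10 mL syringes to 30 mL for both creams.
2. In 7.2, instruct subjects to continue twice-daily application until the end-of-period visit, and amend the two-week wording in 1.1 and 5.1 to 14 days, up to 15.
3. In 14.1, count Visit 6 as 14 (+/- 1) days from the actual Visit 4 date, so that no period exceeds 15 days. Visit 6 then falls between Day 13 + 13 = 26 and Day 15 + 15 = 30. Visit 7 should follow the rule already in 1.1: "subjects will attend a follow-up visit seven (7) days following the last dose of investigational cream".

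Check: with 30 mL and a first application at dispensing, the 30th falls at 29 × 12 = 348 h, which is 360 − 348 = 12 h before a Day 15 visit.

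Cost: 2 mL more of each cream per subject, which is 40 × 2 × 6.2 = 496 mg CBD in all; no extra syringes; up to one extra day of dosing per condition; and a short amendment that can go with the next one. At 15 days the margin is 30 − 30 = 0 mL, so nothing is left for residue in the syringe. A fourth syringe (32 mL in total) would leave 2 mL, at 40 × 4 × 6.2 = 992 mg CBD and 40 × 2 = 80 extra syringes.

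Allowing the end-of-period visits no later than 14 days after dispensing would also close the gap, but every visit one day late would become a deviation, so I would not prefer it.

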7.3 Preparation/Handling/Storage/Accountability

7.3.1 Acquisition and Accountability

The investigational drugs (CBD with Shea butter and Shea butter control) will be stored in a secure area within the UVA Hand Center. Study drug accountability will be maintained by the research team. The investigational drugs will be distributed to the subjects by the study team and are returned to the study team at the next visit. Any remaining investigational drugs will be destroyed in accord with institutional policies.

7.3.2 Formulation, Appearance, Packaging, and Labeling

Hemp Isolate (CBD) will be used from Eco-X, Inc. ([name]). The product is rated for personal care products formulations and the product was tested by Desert Valley Testing.

In the [name] Laboratory at the University of Virginia, the CBD will be mixed to the final desired concentration with USDA Organic Shae butter (Mary Taylor Naturals, LLC, [name]). The control group will receive USDA Organic Shae butter only.

Instructions on how to apply and remove the creams will be provided and explained to subjects. Investigational product will be labeled appropriately for the product to be administered for home use. Minimum labeling requirements include space for subject identification (name or other ID), product name/strength/beyond use date, basic instructions for use, emergency contact information and protocol number. The subjects will be instructed to store the cream at room temperature, and to keep the product out of reach of children.

Notes: This study is using a plant derived cannabinoid (phytocannabinoid) preparations containing CBD. Phytocannabinoid preparations unlike chemically-synthesized cannabinoids, also contain low levels of non-cannabinoid constituents of the Cannabis plant that belong to miscellaneous groups of natural products (primarily terpenoids and flavonoids). The low levels of these adjuvants in the purified material may contribute to the analgesic, as well as the anti-inflammatory effects of Cannabis extracts, but for all intents and purposes are below levels that would be considered therapeutically relevant. Plant derived CBD is identical chemically to endocannabinoids (present endogenously in human or animal tissues) and synthetic CBD. The majority of all CBD containing products on the commercial market are prepared with phytocannabinoid preparations of varied purity.

7.3.3 Product Storage and Stability

The case and control creams are stored by the research team at the UVA Hand Center at room temperature and protected from light. The creams will be used in the study within six (6) months from formulation. After formulation and packaging in the [name] Laboratory, no further preparation such as thawing, diluting, mixing, and/or reconstitution will be required.

7.4 Study Intervention Compliance

Subjects will be instructed to return all tubes containing the control or CBD Cream to the study team at each visit.

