8.2 Participant Discontinuation/Withdrawal

Participants are free to withdraw from participation in the study at any time upon request.

A participant's study treatment would be discontinued for the following reasons:

- Significant study intervention non-compliance
- If any clinical adverse event (AE), laboratory abnormality, or other medical condition or situation occurs such that continued participation in the study would not be in the best interest of the participant
- Disease progression which requires discontinuation of the study intervention
- If the participant meets an exclusion criterion (either newly developed or not previously recognized) that precludes further study participation
- Participant decision to withdraw from study treatment and/or the study.

The reason for participant discontinuation or withdrawal from study treatment will be recorded. Participants who sign the informed consent form and are randomized but do not receive the study intervention may be replaced. Participants who sign the informed consent form, and are randomized and receive the study intervention, and subsequently withdraw, or are withdrawn or discontinued from the study, will not be replaced.

Participants that withdraw from the study (not only from study treatment, but all study follow-up) will not be contacted for any further study visits.

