8.3 Procedures for Discontinuation of Study Intervention

Discontinuation from study treatment means that the subject is withdrawn from the study. In the event of study discontinuation, the participant will not be contacted for any further study visits.

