9.2 Safety Assessments

Medical History: Relevant medical history, including history of mental illness, drug or substance abuse, history of hemp-based product usage and other pertinent history will be recorded in the case report form.

Laboratory Testing: At baseline and Study Day 35, blood draws will be performed on all subjects at the UVA Medical Laboratory. The following tests will be ordered and monitored for clinical abnormalities:

- CBC
- Basic metabolic panel (i.e., BUN, creatinine, CO₂, Cl, K, Na, and glucose)
- Hepatic function testing (i.e., serum transaminases [ALT/AST], total bilirubin, and alkaline phosphatase)
- Pregnancy Testing (if applicable) (Screening)
- Urine Pregnancy Test (if applicable) (Screening and Day 0 before dosing)

Daily Skin Monitoring: Subjects will be asked to observe the testing site for physiologic changes, skin changes or other adverse events daily. Subjects will be provided with a daily diary to record and monitor any observed changes. The daily diary is provided in Appendix 14.3. They will be instructed to notify the investigator of any sudden changes in skin appearance or increase in their arthritic symptoms that are more than minimally tolerated.

Physician Skin Monitoring: At baseline and at every subsequent visit, the investigator will assess the CBD cream site for adverse events. A score will be given corresponding to the assessment tool below:

Score	Definition
0	No erythema
1	Minimal erythema
2	Moderate erythema with sharply defined borders
3	Intense erythema with or without edema
4	Intense erythema with edema and blistering/erosion

- NOTE: Changes in skin appearance will be evaluated using the standardized skin assessment tool above. A patient will be removed from study with a score ≥ 2 .

Clinical Evaluations: Subjects will be monitored weekly for the following:

- Vital sign assessments (i.e., heart rate and blood pressure)
- Suicidal behavior and thoughts as a specific question using the Columbia-Suicide Severity Rating Scale (C-SSRS). The full questionnaire is provided in Attachment 3 (Appendix 14.4).
 - Monitor for somnolence and sedation and advise patients not to drive or operate machinery until they have gained sufficient experience on study drug. Subjects will be asked if they feel more, less, or no change in their level of fatigue during the time they were administering study drug.

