14.3 Daily Sin Monitoring Diary

Day X	Time of onset	Time of symptom improvement	Time of symptom resolution
Itching			
Redness			
Red bumps/hives			
Swelling			
Diarrhea			
Nausea			
Change in appetite			
Fatigue			
Other concerning signs/symptoms			

Signature:

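### Must the plan say what is measured from the returned tubes, given that significant non-compliance can end a subject's participation?

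*Combined protocol and SAP*

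**What the plan says.** Section 7.4 reads in full: "Subjects will be instructed to return all tubes containing the control or CBD Cream to the study team at each visit". Section 7.3.1 makes the research team responsible for accountability and says that the products "are returned to the study team at the next visit. Any remaining investigational drugs will be destroyed in accord with institutional policies". In the Schedule of Activities (Section 14.1) the row "Study Medication Collected" is marked at Days 7, 14, 21 and 28, each with a window of one day either way. Dispensing is marked at Days 0 and 14 only. Section 7.2 supplies 28 mL, to be applied as 1 mL twice daily, and Section 5.1 makes each condition two weeks long.

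The diary serves another purpose. Section 9.2 says "Subjects will be provided with a daily diary to record and monitor any observed changes", and the form in Section 14.3 runs from itching to "Other concerning signs/symptoms", with columns for onset, improvement and resolution. It has no line for applications.

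On consequences, Section 8.2 lists "Significant study intervention non-compliance" among the reasons to stop study treatment, requires the reason to be recorded, and says that treated participants who "subsequently withdraw, or are withdrawn or discontinued from the study, will not be replaced". Section 8.3 adds: "Discontinuation from study treatment means that the subject is withdrawn from the study". No further visits follow.

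Section 11.1 plans a within-subject comparison with the Wilcoxon signed-rank test. Section 11.2.2 defines a population for safety only.

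**The concern.** A rule that removes subjects seems to rest on a quantity the plan never collects. If no amount is recorded, two staff members could apply the rule differently and nobody could check afterwards. A subject removed in the first condition has no score for the second and drops out of the within-subject comparison. Cream use may itself depend on relief or on skin reaction, so the pairs that remain could be a selected group. If nobody is removed, a null result could not be told apart from low use.

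The handling of tubes adds to the doubt. Collection at Days 7 and 21 with no dispensing at those visits could be read as leaving subjects without cream for half of each condition.

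**Working it through.** **1. Supply.** Inputs from Sections 5.1, 7.1 and 7.2: 1 mL twice daily, 14 days, 6.2 mg/mL.

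- Volume: 1 × 2 × 14 = 28 mL, as stated.
- CBD per day: 2 × 6.2 = 12.4 mg, as stated.

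**2. Does cream go back at Days 7 and 21?** Compare the two readings.

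- *Kept by the team.* A subject could use 2 × 7 = 14 of 28 mL, or 50% (12 to 16 mL, 43% to 57%, for 6 to 8 days). The collection mark at Day 14 would have nothing to collect from the first condition. Visit 7 would fall 14 days after the last application (34 − 22 = 12 to 36 − 20 = 16 with windows).
- *Brought in and used on.* All 28 mL can be used over the 14 days, and the marks at Days 14 and 28 have a purpose. Visit 7 falls 7 days after the last application (34 − 29 = 5 to 36 − 27 = 9 with windows), which matches the follow-up interval in the Synopsis.

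Sections 1.1, 5.1, 7.2 and 14.1 agree with one another only on the second reading. The hand-back step is unstated, but the sections do not contradict one another once it is supplied.

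**3. Is there a yardstick for returned cream?** Yes. With full use, the residual is 28 − 2 × days since dispensing, with a floor of zero.

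- Visit 3 (Days 6 to 8): 16 to 12 mL.
- Visit 4 (Days 13 to 15): 2 to 0 mL.
- Visit 6 (12 to 16 days after Visit 4): 4 to 0 mL.

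The extreme case, 24/28 = 85.7% apparent use by a fully compliant subject, needs Visit 4 on Day 15 and Visit 6 on Day 27. It disappears once actual visit dates are used.

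**4. Size of the possible loss.** The documents give no rate, so 5%, 10% and 20% of 40 subjects are assumptions. Each withdrawal is counted as a lost pair.

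| Withdrawn | Pairs left | Standard error ratio √(40/left) | Selection ratio 1/(1 − p) |
|---|---|---|---|
| 2 (5%) | 38 | 1.026 | 1.05 |
| 4 (10%) | 36 | 1.054 | 1.11 |
| 8 (20%) | 32 | 1.118 | 1.25 |

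The last column is the mean difference in those who remain, divided by that in all randomized. It further assumes that those withdrawn have exactly zero CBD–control difference.

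These figures are upper bounds. Outcomes are scheduled at Days 7, 14, 21 and 28 (Section 9.1). A subject stopped at Day 21 may already have a second-condition score, and one stopped at Day 28 loses no efficacy visit. If, as an illustration, withdrawals fell evenly over the four visits, only half (1, 2 or 4) would lack any second-condition score. The ratios would then be √(40/39) = 1.013, √(40/38) = 1.026 and √(40/36) = 1.054. The ratios also describe a paired mean, whereas the planned test is the signed-rank test.

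**5. Against the planned size.** Section 11.2 needs at least 16. With an effect of 0.5 and a variance of 0.25, the two-group formula gives 2 × (1.96 + 0.84)² × 0.25 / 0.5² = 15.7, or 16 per group and 32 in all. A paired formula with a standard deviation of differences of 0.5 gives 7.8, or 8. Even the worst assumed case leaves 32 pairs, so no shortfall against the plan's own requirement is shown.

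**The case for a change.** The strongest case for a change is that it is cheap and that the lost information cannot be recovered. The tubes are already in hand at each visit, one form field would record the residual, and once leftovers are destroyed nothing can be reconstructed. Safety data are also affected. Section 9.2 and the Schedule of Activities place the only post-baseline blood draw at Day 35, so a subject withdrawn for non-compliance would have no laboratory result after exposure.

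Part of this stands. The visible text states neither a measurement nor a meaning for significant non-compliance, and a summary of use by condition would help in reading a null result. Three points limit it.

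- It is not known that amounts go unrecorded. Section 7.3.1 promises accountability, and Section 12.2.1 refers to source worksheets and case report forms that are not reproduced. Section 8.2 requires the reason for each discontinuation to be recorded, so use of the rule can be traced, though not against a threshold.
- The loss of later scores and of the Day 35 blood draw comes from Section 8.3 and applies to every discontinuation, including removal for a skin score of 2 or more. The missing efficacy population is equally general. Neither is a fault of the compliance section.
- A measured residual would not settle actual use. Cream is dispensed into a gloved hand (Section 7.2), so volume gone from the syringe is an upper limit on volume applied. Comparing subjects as randomized does not require an adherence measure.

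**Conclusion.** The gap is real but one of wording, and no change to the plan follows. The plan leaves unsaid what is recorded from the tubes, the hand-back at Days 7 and 21, and what counts as significant non-compliance. Staff keeping ordinary accountability records would supply the first. The two-week conditions and 14-day supply imply the second. The third is a judgement for the sponsor and the investigator, and this review proposes no threshold. Analysts can run the signed-rank comparison on the pairs that exist and describe use from whatever the accountability records hold.

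No stated figure is wrong: 28 mL and 12.4 mg per day reproduce exactly, and no better analysis is identified to replace the planned one. The possible loss is at most 2 to 8 of 40 pairs, under an assumed withdrawal rate of 5% to 20% with every withdrawal costing a pair. The 1.05 to 1.25 selection ratio also needs zero effect in those withdrawn. These figures would fit dropout for any reason and are no evidence of a defect in the compliance section. The conclusion assumes that accountability is kept in the usual way, which the visible text promises but does not describe.
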